3.2. Eligibility

Subject eligibility is based on diagnosis of symptoms and signs compatible with DED due to MGD. See the protocol for a complete listing of inclusion/exclusion criteria.

3.3. Analysis Populations

The per-protocol analysis population includes all subjects who have at least one follow-up visit and have no major protocol deviations. The primary and secondary endpoint analysis will be performed based on the per-protocol population.

The intent-to-treat (ITT) analysis population includes all subjects who are randomized to either arm, regardless of treatment received.

4. Study Evaluations

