2.7. Concurrent Control

Subjects will be randomized 1:1 to a study arm and to a control arm. Subjects in the control arm will undergo exactly the same procedures as subjects in the study arm, with the exception that the IPL pulses will not be actually delivered. This applies to both test spots and the full treatment.

Due to the nature of the IPL treatment, it is not possible to ensure masking of the subjects, as subjects are generally aware that IPL treatment should be felt and should normally leave a temporary redness of the skin. This said, the following steps will be taken:

In the informed consent process, subjects will be told that in some cases the IPL treatment might be felt as a mild pain/discomfort on the skin, and that the treatment can cause redness of the skin that should disappear within a few minutes. During IPL administration, all subjects will wear protective goggles that will completely occlude their vision.

In the control arm, subjects will undergo a sham treatment that will mimic the IPL (IPL) therapy. The sham treatment will be implemented using a filter that blocks all light emitted by the M22-IPL (the ∞ filter described in the protocol). The tip of the lightguide will still be cooled and the device will still produce clicking sounds whenever the trigger button on the IPL handpiece is triggered, but no light will be actually transmitted to the skin. Following the sham IPL procedure, subjects will undergo meibomian gland expression.

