2.8. Blinding

Every effort will be made to ensure examiners measuring primary outcomes are masked to the treatment allocation. However, due to the nature of the IPL treatment, it is not possible to completely ensure masking of the examiner. The examiner that will assess the outcome measures at the baseline visit and at the follow-up visit will not be the study investigator that will administer the IPL pulses. This will increase the probability that the examiner is masked to the allocation.

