5.3. Sample Size

Approximately 4 months after initiation of the study, a round of site monitoring visits revealed that one of the three sites in the study was not following the instructions above with respect to where the M22 IPL lightguide should be applied; for IPL and sham subjects the lightguide was being applied too far from the eyelid margin in contrast to what is described in Figure 5 above. As a result, it is possible that the IPL treatments among the initial cohort of subjects at that site was will prove to be ineffective, or of reduced effectiveness compared to the sham control. The lightguide was applied correctly at the other two sites.

Although no data were unmasked, soon after this issue was recognized by study monitors, Lumenis initiated a corrective action (retraining and greater emphasis in the protocol), to better assure the protocol instructions would be followed.

To restore the original statistical power, the sample size was increased. Below are the original and adjusted calculations of the sample size:

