5.3.1. Original calculation of the sample size

Assuming a 1:1 randomization ratio, a mean of 5 ± 5 sec for \triangle TBUT of the study arm, a mean of 1 ± 5 sec for \triangle TBUT of the control arm, an alpha level of 0.05 and a power of 80%, the total sample size is 50 completed study eyes (25 for the study arm and 25 for the control arm). Assuming a dropout rate of 15%, the anticipated number of enrolled subjects is 58. Assuming a screening failure rate of 15%, the anticipated total number of screened subjects is 66.

In addition, MGD is less common without concomitant skin rosacea. Therefore, enrollment will continue until at least 10 subjects without skin rosacea are enrolled, even if 58 subjects were already enrolled.

5.3.2. Adjusted calculation of the sample size.

After the corrective action to remedy the treatment errors, the sample size was recalculated using a simulation where we made the following conservative assumptions:

- The initial 8 IPL subjects at the affected site had response equal to the control arm (1±5 seconds)
- Subsequent to the corrective action, IPL subjects at the affected site had a response equal to the IPL arm (5±5 seconds)
- The final analysis was ITT, which included the inappropriately treated patients in the IPL arm.
- The correlation between eyes within a subject is 0.5.

Under these assumptions the overall treatment effect is "diluted" by the initial set of patients who were treated inappropriately. Under these conservative assumptions, the sample size needed to restore the original power was calculated to be 136 evaluable eyes (68 subjects, i.e. 18 subjects more than the original 50 subjects).

In addition, in order to allow for full comparison of the effect of the corrective action, 15 patients were added to the enrollment at the affected site so there would be sufficient before/after patients to allow for clinical evaluation of the difference.

Adding these 33 (18+15) subjects to the original 50 completed subjects, the number of completed subjects is up to 83. Therefore, with a loss to follow-up rate of 7% the expected number of enrolled subjects is 89, and with a screening failure rate of 23% the expected number of screened subjects is 116.

All sample size re-calculations were done prior to any unmasking of any results from the study.

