5.7.1. Stratified Analysis

To account for the potential loss of IPL treatment effect at one site (hereafter called "A") a stratified analysis will be performed that includes a separate stratum comprising subjects at site A who were treated prior to the corrective action. The strata will be labeled as A1, A2, B, and C for sites A, B, and C, with A1 and A2 the two separate groups of patients at site A before and after the corrective action. Since the treatment is applied over a sequence of four visits, we will conservatively assign to stratum A2 only those patients who received all four of their treatments subsequent to the corrective action. Any patient who received any one of their four scheduled treatments prior to the corrective action will be assigned to stratum A1.

Stratum	Corrective Action	Description
A1	No	Patients from site A with one or more treatment visits prior to the corrective action

Thus, the following four strata are obtained:

A2	Yes	Patients from site A with all 4 treatment visits subsequent to the corrective action
В	No	Patients from site B
C	No	Patients from site C

An ANOVA analysis will be performed for the change in TBUT primary endpoint, with fixed effects for treatment and stratum and a random subject effect.

To examine the effect of the corrective action, we will group the strata into two sets: {A1}, for the pre-corrective-action subjects at site A, and {A2+B+C} for all post-corrective-action subjects at site A, combined with all subjects at B or C. We will test for significance of the corrective action by creating a 1 degree of freedom contrast for "treatment by corrective action", using treatment (1 df) and the two corrective action sets (1 df), and test whether the contrast is significantly different from 0, using a two-sided alpha of 0.15.

- If the contrast is not significant, then the results will be analyzed as planned, pooling across all strata pre- and post- corrective action.
- If the contrast is significant then we will carry out the analyses separately for A1 and for the combined {A2+B+C}.

We will also directly compare outcomes between A1 and A2 by calculating the LSM for the difference between the two, along with the associated 95% CI.

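### SAP 3.3 makes a per-protocol set with no definition of a major deviation primary and gives ITT no analysis, although the trial was re-sized for an ITT final analysis that keeps the mistreated IPL subjects

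*SAP*

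**What the plan says.** SAP 3.3 defines two populations. Per-protocol requires at least one follow-up visit and no major protocol deviation. ITT is everyone randomised, whatever treatment was received. Only the first is used: "The primary and secondary endpoint analysis will be performed based on the per-protocol population". Neither document defines a major deviation, says who classifies deviations, or says when. The protocol names no per-protocol set. Protocol 4.1 and SAP 3.1 do say that the aim is to analyse subjects who finished the schedule.

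The sizing text rests on a different population. SAP 5.3.2 and protocol 7.3.2 list, among the assumptions behind 68 subjects, that "The final analysis was ITT, which included the inappropriately treated patients in the IPL arm". They then take the total to 83: "15 patients were added to the enrollment at the affected site so there would be sufficient before/after patients".

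The deviation at issue is known. At site A, "for IPL and sham subjects the lightguide was being applied too far from the eyelid margin" (SAP 5.3). SAP 5.7.1 and protocol 7.4.1 put the subjects treated before the correction in stratum A1. They test a treatment-by-corrective-action contrast at two-sided 0.15. If it is not significant, the analysis proceeds "pooling across all strata pre- and post- corrective action". If it is, "we will carry out the analyses separately for A1 and for the combined" remaining strata. A1 is also compared directly with A2.

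**The concern.** The general rule in SAP 3.3 and the specific rules in SAP 5.3.2 and 5.7.1 cannot all operate if misplacement is a major deviation. A1 would then hold nobody in the primary population, so the pooling, the contrast and the A1 versus A2 comparison could not be run. The 15 subjects added for the before/after comparison would lose their purpose.

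At stake is the question that the headline result answers: the effect of IPL as assigned, or of IPL delivered as instructed. The re-sizing was justified for the first. The SAP is dated 3/26/2020. The misplacement already appears in protocol revision C, effective September 2019, so the SAP could have said how it is classed. The SAP also concedes that "it is not possible to ensure masking of the subjects" and that "it is not possible to completely ensure masking of the examiner". In such a trial, exclusions made after randomisation need a rule that is written down and applied without knowledge of arm. The SAP requires neither.

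**Working it through.** **Inputs.** From the synopsis and SAP 5.3.1 and 5.3.2: change in TBUT 5 ± 5 s (IPL) and 1 ± 5 s (control), two-sided alpha 0.05, power 0.80, 1:1 allocation, 8 IPL subjects at site A responding like control, correlation between eyes 0.5. The re-sizing assumptions name no covariate, so none is used here.

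**The plan's own figures.**
- Original size, one eye per subject, normal approximation: 2 × (1.960 + 0.842)² × 5² / 4² = 24.5, so 25 per arm and 50 in total, as stated.
- Re-sized trial: the mean of two eyes has SD 5 × √((1 + 0.5)/2) = 4.33 s. With both eyes observed, a t-test on subject means is equivalent to the random-intercept model. With 34 per arm and the 8 kept, the expected difference is 4 × 26/34 = 3.06 s. Simulation gives power 0.80, which reproduces the stated 68. At 50 subjects with the 8 kept, it is 4 × 17/25 = 2.72 s and power 0.55.

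**ITT at 83 (42 IPL, 41 sham).** Expected difference 4 × 34/42 = 3.24 s; power 0.91 by simulation.

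**If misplacement is classed as major.** The 8 IPL subjects leave, and so do the misplaced sham subjects, whose number is not given. Protocol 3.1.1 uses site envelopes in blocks of 2 and 4, opened in order, so the arms at a site differ by at most 2 at any point. If A1 is a consecutive cohort, 8 IPL subjects imply 6 to 10 sham subjects before dropout. That range is an assumption. The expected difference is then 4.00 s, with standard error 4.33 × √(1/n₁ + 1/n₂). Power (noncentral t):

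| Total | 6 sham excluded | 8 excluded | 10 excluded |
|---|---|---|---|
| 83 | 0.966 | 0.961 | 0.956 |
| 68 | 0.914 | 0.904 | 0.892 |
| Smallest even total with power of at least 0.80 | 54 | 56 | 58 |

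So 68 − 58 = 10 to 68 − 54 = 14 of the 18 subjects added to restore power rest on an ITT analysis.

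**If misplacement is not major, and nothing else is.** The per-protocol set is everyone with the follow-up visit, A1 included. The expected difference at 83 is 3.24 s, the same as under ITT.

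**The SAP 5.7.1 branch (separate point).** At 83 subjects with 8 IPL and 6 to 10 sham in A1, the contrast of the four cell means (79 df) has expectation 4 s. Its standard error is 4.33 × √(1/8 + 1/34 + 1/s + 1/(41 − s)), where s is the number of sham subjects in A1. That is 2.56 s for s = 6 and 2.32 s for s = 10. By simulation it is significant at 0.15 in about 55% to 61% of trials. In about 4% to 5% it is significant, the pooled test fails and {A2+B+C} succeeds, so the missing decision rule settles the outcome.

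**The case against.** The best defence is that the specific text governs. SAP 5.7.1 and the 15 added subjects presuppose that A1 is analysed, so misplacement cannot have been meant as a major deviation. On that reading, and with no other major deviations, the per-protocol set is all subjects with follow-up and the expected estimate is unchanged. This stands as far as it goes: the move to 4.00 s is conditional. But the reading is an inference, and SAP 3.3 gives nothing to support it.

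Second, ITT in SAP 5.3.2 shows only that mistreated subjects are kept. The sizing counts evaluable eyes, and SAP 3.1 speaks of subjects who finished the schedule, so an analysis of all randomised subjects with missing outcomes handled was not clearly intended. That also stands. It means the missing-data rule is needed mainly because ITT becomes primary, and that SAP 3.1 must be amended too.

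Third, a reader might infer that the population was chosen with results in view, or that deviations would be classified unmasked. The documents do not support this. They say that no data were unmasked when the problem was recognised and that all re-sizing came before unmasking. The masking caveats in SAP 2.7 and 2.8 concern subjects and examiners during conduct. On classification of deviations the documents are silent, and that silence is the defect.

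**Conclusion.** The contradiction is in current text and governs the primary analysis, so it must be fixed before unmasking. On the plan's assumptions, the choice of population moves the expected difference at 83 subjects from 3.24 s to 4.00 s (4.00/3.24 = 1.24, about 24% larger) if misplacement is classed as major, and not at all if it is not and no other deviation is major. Which of these applies is not stated.

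A reader might infer that the per-protocol rule costs power or in itself inflates type I error. Neither follows: power is higher with the exclusions (about 0.96 to 0.97 against 0.91 at 83), and dropping A1 by one rule in both arms does not in itself raise the error rate. Nor do the figures show that all 18 added subjects depend on ITT; with 6 to 10 sham subjects excluded, 10 to 14 do.

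The figures rest on the plan's response assumptions, an assumed sham count in A1, and complete follow-up data. The undecided branch in SAP 5.7.1 is a lesser, separate gap that exists whichever population is primary.

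**What to change.** **SAP 3.3.** Make ITT, meaning all randomised subjects in their assigned arm including A1, the population for the primary and secondary endpoints, with per-protocol supportive. List the major deviations, apply one rule to both arms, classify them masked to arm before unmasking, and state whether the site A misplacement is on the list.

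**SAP 3.1 and protocol 4.1.** Reword the aim of analysing schedule completers to agree.

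**SAP 5.7.** Fix, before unmasking, a rule for randomised subjects without follow-up TBUT and one sensitivity analysis; multiple imputation is one option. SAP 5.4 only accounts for dropouts. State that follow-up data obtained from withdrawn subjects (protocol 3.2) are used.

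**SAP 5.7.1 and protocol 7.4.1 (lesser point).** State which result decides success if the 0.15-level contrast is significant. The pooled ITT result is one option and matches the sizing basis.

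**Cost.** Wording, a deviation list with masked classification, and some code; no new subjects. With 89 randomised and 6 lacking follow-up, ITT power from the observed subjects is about 0.90 to 0.91, depending on which arm loses them and assuming that any missing IPL subjects were correctly treated. That is above the planned 0.80, although a conservative sensitivity analysis would show less. The expected estimate falls only relative to a per-protocol set that would have excluded A1.

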4.1. Effectiveness

4.1.1. Primary effectiveness endpoint

The primary efficiency endpoint will be estimated as the difference in the *change* of TBUT from baseline to follow-up (10 weeks) between the study arm and the control arm, where the change of TBUT is defined as TBUT at the follow-up minus TBUT at the baseline.

A linear mixed-effect (LME) model will be used to test the null hypothesis that the changes of TBUT are not different between the two arms. The success criterion will include the following two conditions:

- 1. Two-sided p-value < 0.05
- 2. The change of TBUT in eyes of the study arm is *larger* than the change of TBUT in eyes of the control arm

The linear mixed-effect model will include a random effect for subjects to account for correlation between eyes within subjects.

4.1.2. Secondary effectiveness endpoints

The following secondary efficiency endpoints will be estimated:

- The difference in the *change* of EDS, between subjects in the study arm and subjects in the control arm
- The difference in the *change* of OSDI, between subjects in the study arm and subjects in the control arm

where *change* is defined as the value of the variable (OSDI or EDS) at the follow-up minus the value of the variable at the baseline.

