 Ocular surface abnormality that may compromise corneal integrity in either eye (e.g., prior chemical burn, recurrent corneal erosion, corneal epithelial defect, Grade 3 corneal fluorescein staining, or map dot fingerprint dystrophy)
• Eyelid abnormalities that affect lid function in either eye, including: entropion, ectropion, tumor, edema, blepharospasm, lagophthalmos, severe trichiasis, and severe ptosis
 Any systemic condition that may cause dry eye disease, including: Stevens-Johnson syndrome, vitamin A deficiency, rheumatoid arthritis, Wegener's granulomatosis, sarcoidosis, leukemia, Riley-Day syndrome, systemic lupus erythematosus, and Sjögren's syndrome

	• Unwilling or unable to abstain from the use of medications known to cause dryness (e.g., isotretinoin, antihistamines) throughout the study duration. Subjects must discontinue these medications for at least 1 month prior to the baseline visit.			
	Any condition revealed whereby the investigator deems the subject inappropriate for this study			
	Primary objectives TBUT estimated at the single FU (Between 4 weeks -3 days and 4 weeks + 7 days after the final treatment)			
Objectives	Measurement of TBUT will be implemented using FUL-GLO® fluorescein ophthalmic strips. Three successive readings will be taken and averaged to a single value.			
	Secondary objectives Self-evaluation of OSDI at the single FU, using the OSDI questionnaire Self-evaluation of Eye Dryness Score (EDS) at the single FU, using a VAS			
	Primary endpoint:			
	The difference in the change of TBUT from BL to FU, between eyes in the study arm and eyes in the control arm			
	The improvement of TBUT in eyes of the study arm is larger than the improvement of TBUT in eyes of the control arm, where improvement is defined as a positive change of TBUT from BL to FU			
	Secondary endpoints			
Criteria for Evaluation	The difference in the change of OSDI from BL to FU, between subjects in the study arm and subjects in the control arm			
	The difference in the change of EDS from BL to FU, between subjects in the study arm and subjects in the control arm			
	The improvement of OSDI in the study arm is larger than the improvement of OSDI in the control arm, where improvement is defined as a negative change of OSDI from BL to FU			
	arm, where improvement is defined as a negative change of OSDI from BL to FU			

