	6. Self-assessment of pain/discomfort during IPL administration, using a VAS			
	7. Self-assessment of pain/discomfort during MGX, using a VAS			
	There will be a single follow-up (FU) visit, which will occur 4 weeks (-3 days, + 7 days) after the final treatment session. Subjects will undergo the following assessments, in the specified order:			
	 Subject's report of the daily usage (frequency and dose) of eye drop, warm compresses and lid hygiene since the previous visit 			
	2. Three consecutive measurements of TBUT in both eyes			
Follow-up (FU)	3. Routine ophthalmology tests in both eyes, including: biomicroscopy, BCVA and IOP			
visit	4. OSDI, self-assessed using an OSDI questionnaire			
	5. EDS, self-assessed using a VAS			
	6. High resolution close-up photos of both eyes, including: iris, lid margins and eyelashes			
	7. Meibography of the upper and lower eyelids in both eyes			
	8. Meibomian gland secretion (MGS) score in 15 glands of the lower eyelid in both eyes			
Safety outcome measures	 incidence of non-ocular adverse events throughout the study incidence of ocular adverse events throughout the study incidence of unanticipated serious adverse events throughout the study self-assessment of pain/discomfort of IPL in treatment sessions (using a VAS) self-assessment of pain/discomfort of MGX in treatment sessions (using a VAS) 			
Covariates	Baseline TBUT (continuous)Baseline skin rosacea (4-point scale)			
	The following assumptions were used to calculate the original sample size:			
Sample Size	(1) In the study arm, the change of TBUT from BL to FU \approx 5 \pm 5 sec (2) In the control arm, the change of TBUT from BL to FU \approx 1 \pm 5 sec			

	(3) A type I error of 0.05 (two-tailed test)				
	(4) A type II error of 0.2 (power = 0.8)				
	(5) A 1:1 ratio of Treatment to Control				
	With these assumptions, the minimal sample size was calculated to be 50 evaluable subjects (100 evaluable eyes): 25 subjects (50 eyes) in the control arm and 25 subjects (50 eyes) in the study arm.				
	Assuming a dropout rate of 15%, the anticipated number of enrolled subjects was 59. Assuming a screening failure rate of 15%, the anticipated total number of screened subjects was 69.				

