A previous study demonstrated that in subjects with a lower TBUT at the baseline, the change in TBUT at the follow-up was larger [21]. Although not shown in this study, the severity level of skin rosacea at the baseline may also be a confounder. Hence, in addition to the primary analysis, we will carry out an analysis of covariance (ANCOVA) to adjust for these covariates.

The following baseline covariates will be included in the ANCOVA:

- (1) TBUT at baseline. This covariate will be treated as continuous.
- (2) The 4-point severity level of skin rosacea at baseline (0= none; 1 = mild; 2 = moderate; 3 = severe). This covariate will be treated as either a numeric score (continuous) or using orthogonal polynomial contrasts.

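### OSDI, EDS and MGS changes are compared without adjustment for their own baselines, although these are collected; adding the term costs only wording and usually improves precision

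*SAP*

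**What the plan says.** - **Endpoints.** SAP 4.1.2 and the SAP synopsis define the secondary endpoints as between-arm differences in change. For OSDI the synopsis reads "The difference in the change of OSDI from BL to FU, between subjects in the study arm and subjects in the control arm". A change, in SAP 4.1.2, "is defined as the value of the variable (OSDI or EDS) at the follow-up minus the value of the variable at the baseline".
- **Tests.** SAP 5.7, with the same text in Protocol 7.4, gives OSDI a paired t-test on change and EDS a mixed model with a random subject intercept. Other eye-level continuous outcomes, which include MGS, get a mixed model or a two-sample t-test. No baseline term is named for any of them.
- **Covariates.** SAP 5.7 adds an ANCOVA on top of the primary analysis. Its first covariate is "TBUT at baseline. This covariate will be treated as continuous"; its second is rosacea severity on a four-point scale. Baseline OSDI, EDS and MGS are not listed.
- **TBUT.** The coded model in SAP 5.7.2 regresses the TBUT change on treatment and baseline TBUT.
- **Baselines.** SAP 5.5 summarises baseline OSDI, EDS and MGS by arm and has them assessed for balance. It does not say what follows if they are unbalanced.

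**The concern.** SAP 5.7 justifies adjusting TBUT on the ground that subjects who start lower change more. The same reasoning applies to symptom scores and gland scores, yet the adjustment stops at TBUT. OSDI and EDS carry the symptom objective in SAP 1.2, and all of the sizing is for TBUT, so their precision is whatever the TBUT sample happens to give.

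Two things are at stake. The first is precision: if baseline predicts follow-up, a raw change score usually carries variance that a baseline term would remove. The second is chance imbalance: if one arm happens to start worse, part of the difference in change reflects that start. Because SAP 5.5 has a balance check but no rule, the decision to adjust could also end up being made after the data are seen.

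This is separate from the choice of OSDI test. Replacing the paired t-test with a two-sample t-test on change would give a between-arm comparison, but still an unadjusted one.

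**Working it through.** **1. The plan's own figure.** SAP 5.3.1 assumes TBUT changes of 5 and 1 s, SD 5, alpha 0.05 (two-tailed in the synopsis), power 0.80 and 1:1 allocation. Per arm, n = 2(1.960 + 0.842)² × 5²/4² = 24.5, so 25 per arm and 50 in total, as stated. (An exact two-sided t calculation gives power 0.791 at 25 per arm.) No comparable figure exists for OSDI, EDS or MGS.

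**2. Inputs for this point.** From the documents: 83 evaluable subjects, entry at OSDI ≥ 23, and MGS ≤ 12 in the study eye. Not given, so assumed: the baseline-to-follow-up correlation r and the SDs s0 (baseline) and s1 (follow-up). The only correlation in the SAP, 0.5, is between eyes and is a different quantity.

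**3. Variance.** The comparator is a between-arm test of raw change.

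- Var(change) = s0² + s1² − 2·r·s0·s1
- Residual variance after baseline adjustment = s1²(1 − r²)
- Share removed = (s0 − r·s1)² / Var(change), which cannot be negative
- With s0 = s1 this becomes (1 − r)/2

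| s0/s1 | r = 0.3 | r = 0.5 | r = 0.7 |
|---|---|---|---|
| 0.6 | 9% | 1% | 2% |
| 0.7 | 15% | 5% | 0% |
| 0.8 | 22% | 11% | 2% |
| 1.0 | 35% | 25% | 15% |
| 1.2 | 47% | 40% | 33% |

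In the equal-SD row, 83 adjusted subjects are worth 83/0.65 = 128, 83/0.75 = 111 and 83/0.85 = 98 unadjusted ones. A change-score test with 80% power would have 93.5%, 89.9% and 86.0%.

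**4. Effect of the OSDI entry cut.** Simulated with an assumed unselected SD of 20 and truncation at 23:

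| Unselected mean | r = 0.5 | r = 0.7 |
|---|---|---|
| 30 | 12.8% | 7.3% |
| 40 | 16.3% | 9.4% |
| 50 | 19.6% | 11.5% |

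The r shown is before truncation. The cut shrinks s0 relative to s1, so the gain is smaller than in the equal-SD row.

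**5. Chance imbalance.** Given an observed baseline difference d, the change contrast is expected to shift by −(1 − slope)·d, where slope = r·s1/s0. With equal SDs, r = 0.5 and d = 5 OSDI points, the shift is −0.5 × 5 = −2.5 points. If the baseline OSDI SD is 15–20 (assumed) with 41 per arm, the SE of d is SD·√(2/41) = 3.3–4.4, so a gap of 5 or more in either direction has probability of about 13–26%.

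**6. Simulation.** 84 subjects, 20,000 replicates, equal SDs, true effect −0.50 SD:

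| | r = 0.3 | r = 0.5 | r = 0.7 |
|---|---|---|---|
| Unadjusted, all replicates | −0.500 | −0.499 | −0.501 |
| Unadjusted, d above +1 SE | −0.73 | −0.67 | −0.60 |
| Adjusted, d above +1 SE | −0.50 | −0.50 | −0.50 |
| Variance ratio, adjusted/unadjusted | 0.661 | 0.766 | 0.859 |

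The type I error of the unadjusted two-sample test of change (r = 0.5) was 0.049. The variance ratios sit slightly above the theoretical 0.65, 0.75 and 0.85; that 1–2% is the price of estimating the slope.

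**The case against.** The strongest reply is that nothing here is invalid. Subjects are randomized 1:1, regression to the mean acts on both arms, and the unadjusted contrast averages to the true effect with correct type I error. That stands. A reader might infer that the omission biases the symptom comparison; the documents do not support this. What shifts is the estimate given a particular observed imbalance, and it can go either way. One limit applies: the on-average guarantee belongs to the randomized set, whereas SAP 3.3 analyses the secondary endpoints per protocol.

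A reader might also take 15–35% as this trial's loss. It is not: it needs r between 0.3 and 0.7 and equal SDs, and the documents give neither.

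Nor do the entry criteria make the gain larger. Under a linear relation, selecting on baseline leaves the slope unchanged and reduces the baseline SD, which usually lowers the saving. For MGS the study eye is confined to 0–12 on a 0–45 scale, so its baseline SD is at most about 6 while follow-up is unrestricted; the low-ratio rows of the table may be the relevant ones there. EDS has no entry cut.

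Finally, SAP 4.1.2 does not itself exclude adjustment. It only defines change, and SAP 5.7.2 uses the same definition for TBUT with a baseline term. The gap lies in SAP 5.7.

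Study success rests on TBUT alone (SAP 2.2), which limits the weight of the point. It does not remove it, since the remedy needs no new data.

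**Conclusion.** The omission is real: no own-baseline term is specified for OSDI, EDS or MGS, although the baselines are in hand and the SAP adjusts TBUT in this way. The consequence is usually lost precision and sensitivity to chance baseline imbalance; it is not bias on average or an inflated error rate.

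The size cannot be fixed from the documents. With equal SDs it is 35%, 25% or 15% of the variance at r = 0.3, 0.5 or 0.7. Over baseline-to-follow-up SD ratios of 0.6 to 1.2 it runs from about 0% to 47%, and for OSDI it is about 7–20% under the assumed entry-cut scenarios. This is a recommended improvement, not a flaw that invalidates the secondary analyses.

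**What to change.** In SAP 5.7 and Protocol 7.4:

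- **OSDI:** a subject-level linear model, change = arm + baseline OSDI, reporting the arm coefficient with its 95% CI. This also supplies the between-arm test that the hypothesis in SAP 5.2 needs; a paired t-test on change assesses change within subjects.
- **EDS:** the same model with baseline EDS, after reconciling Protocol 5.1.5 (a single score for both eyes) with SAP 5.7 (a score for each eye). If it proves to be per eye, keep the random subject intercept.
- **MGS:** add the eye's baseline MGS to the mixed model.
- **Site:** not required for this point. If a site term is added, use the plan's own strata A1, A2, B and C from SAP 5.7.1.

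The definition of change can stay as it is: regressing change on arm and baseline gives the same arm coefficient as regressing the follow-up value on them. The cost is wording in two documents and one degree of freedom per model. Specifying the term before unmasking also removes any later choice about adjustment after the SAP 5.5 balance check.
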